The laboratory tests listed in [Table 2](#) will be performed by the central laboratory service provider at Visits 1, 2, 4, 6, 8, 10, 12, 16, 20, EOT and at Week 188 follow-up visit ("complete" lab). At Visits 3, 5, 7, 9, 11, 13, 14, 15, 17, 18, 19, 21, only WBC, serum CRP and serum albumin will be collected ("targeted" lab). A local laboratory may be used for selected tests in exceptional cases. Subjects should be fasting for at least 8 hours prior to the blood sample being taken at the "complete" visits, except for screening (see [Appendix C](#)).

Instructions regarding sample collection, sample handling/processing and sample shipping are provided in the Laboratory Manual in the ISF. For time points of laboratory sampling, see [Appendix C](#).

Laboratory results (i.e., all safety laboratory and clinical laboratory data relevant for current clinical practice) of the subjects will be available in real time to the respective investigator (via laboratory reports) and to the sponsor (via the central laboratory website) and selected abnormal laboratory alerts will be flagged to the site and sent to sponsor in real time.

A clinically relevant value may be either in or outside the reference range. Clinically relevant abnormal laboratory test results must be confirmed using an unscheduled visit laboratory kit and should be repeated until normalization or stabilization or until an alternative explanation has been found. Laboratory abnormalities are considered to be adverse events only if they result in discontinuation from the study, necessitate therapeutic medical intervention, and/or if the investigator considers them to be adverse events.

Table 2. Laboratory Tests

Category	Test Name
Hematology	Hematocrit (Hct) Hemoglobin (Hb) Red Blood Cell Count/Erythrocytes White Blood Cells/Leukocytes Platelet Count/Thrombocytes
Diff. Automatic	Neutrophils (relative count) Eosinophils (relative count) Basophils (relative count) Monocytes (relative count) Lymphocytes (relative count)
Diff. Manual (if Diff Automatic is abnormal)	Neutrophils, bands (Stabs) Neutrophils, polymorphonuclear (PMN) Eosinophils Basophils Monocytes Lymphocytes
Enzymes	AST(GOT) ALT(GPT) Alkaline Phosphatase (AP) Creatine Kinase (CK) CK-MB, only if CK is elevated Gamma-Glutamyl Transferase (GGT/γ-GT)
Electrolytes	Calcium Sodium Potassium Chloride Bicarbonate

Table 2. Laboratory Tests (Continued)

Category	Test Name

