4.2 Design Diagram

This trial is a randomized, open-label study of two different dose regimens of risankizumab, 150 mg (2 syringes, 75 mg each) or 75 mg (1 syringe) at Week 0, 4 and every 12 weeks in two populations (subjects with GPP and with EP). Starting after the Week 16 visit, subjects on 75 mg may increase dosage to 150 mg. In total, at least 16 subjects, 8 with generalized pustular psoriasis and 8 with erythrodermic psoriasis will be randomized in this trial. From Week 16, subjects will be uptitrated to 150 mg if they have not achieved a clinical response (for subjects with GPP:at least "Slightly Improved" in the overall improvement rating from baseline according to JDA total score; for subjects EP: at least "Minimally Improved" in Clinical Global Impression-Global Improvement).

Figure 1. Trial Design

All subjects are to adhere to the visit schedule as specified in the Protocol Appendix C. Each visit date (with its window) is to be counted from Day 1. If any visit has to be rescheduled, subsequent visits should follow the original visit date schedule. Additional visits for the purpose of re-testing of laboratory parameters or AE monitoring may be included as deemed necessary by the investigator.

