6.0 Analysis Conventions

Since this is an open-label continuation study, no statistical test will be conducted. Summary statistics will be provided. Data from preceding studies will be integrated with data from this study in the summaries.

Definition of Baseline

For this study, baseline values are defined as the last non-missing values prior to the first dose of study drug in this study. These baseline values will be referred to as "BL" in this document. Unless otherwise specified, this will be the "baseline" for analysis.

Definition of Rx Days (Days Relative to the Date of First Dose of Study Drug)

Rx days are calculated for each time point relative to the date of first dose of this study. They are defined as the number of days between the day of the first dose of risankizumab and the specific time point. Rx days are negative values when the time point of interest is prior to the first risankizumab dose day. Rx days are positive values when the time point of interest is on or after the first risankizumab dose day. The day of the first dose of risankizumab is defined as Rx Day 1, while the day prior to the first risankizumab dose is defined as Rx Day –1 (there is no Rx Day 0).

Definition of Analysis Windows

All time points and corresponding time windows are defined based on Rx Days.

For efficacy analyses, local tolerability, laboratory parameters, and vital sign variables, analysis windows are constructed using the following algorithm:

- Determine the nominal Rx day for each visit (e.g., Week 4 [4 weeks after Baseline visit] equals Rx Day 28).
- In order to include all post baseline data, the first post-baseline interval starts on the first day and the time after the first dose of risankizumab (Rx Day 1).
- Determine the window around a specific nominal Rx day, are presented in the Protocol Appendix C.
- If more than one assessment is included in a time window the assessment closest to the nominal day will be used. If there are two observations equidistant to the nominal day, the one after the nominal day will be used in analyses. If more than one post baseline assessment is included on the same

day, then the worst assessment on that day will be used in analyses, except those specified in Section [11.0](#).

The protocol specified visits and corresponding time windows used in the efficacy analyses, local tolerability, laboratory parameters, and vital sign variables, are presented in the following [Table 1](#) – [Table 32](#).

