11.3.2 Statistical Methods

Analysis of Quantitative Laboratory Parameters (Hematology, Chemistry and Urinalysis)

Though the protocol indicates utilizing the Rheumatology Common Toxicity Criteria (RCTC) scale for grading laboratory values, given that the National Cancer Institute Common Toxicity Criteria for Adverse Events (NCI CTCAE) scale includes a more comprehensive list of laboratory values, the lab analyses based on the NCI CTCAE scale will be presented. Changes from Baseline to each scheduled visit and to the final value in continuous laboratory parameters will be summarized with the mean, standard deviation and median.

If there are multiple post-baseline measurements on the same day, average value will be used.

Shift Tables

Shift tables for changes from Baseline according to the normal range will be provided for each hematology, clinical chemistry and urinalysis (pH only) parameter. Shifts from Baseline to the following endpoints will be considered: minimum value, maximum value and final value. Categories of "low or normal" and "high or normal" will be included at Baseline in addition to the categories of "low," "normal," "high" and "missing." If there are multiple post-baseline measurements on the same day, last value will be used.

Potentially Clinically Significant Laboratory Values

Frequencies and percentages of subjects with post Baseline lab values met the following criteria in [Table 65](#) and [Table 76](#) will be summarized.

Table 65. Criteria for Potentially Clinically Important Chemistry Values

Chemistry Variables	Units	Definition of Potentially Clinically Important Current (Version 4) NCI CTCAE Grade 3 or Greater	
		Very Low	Very High
TBL	mcmol/L		> 3.0 × ULN
ALP	U/L		> 5.0 × ULN
SGOT/AST	U/L		> 5.0 × ULN
SGPT/ALT	U/L		> 5.0 × ULN
Albumin	g/L	< 20	
Glucose	mmol/L	< 2.2	> 13.9
Triglycerides	mmol/L		> 5.7
Creatinine	mcmol/L		> 3.0 × ULN
Sodium	mmol/L	< 130	> 155
Potassium	mmol/L	< 3.0	> 6.0
Calcium	mmol/L	< 1.75	> 3.1
CPK	U/L		> 5.0 × ULN
Total Cholesterol	mmol/L		> 10.34
GGT			> 5.0 × ULN

Table 76. Criteria for Potentially Clinically Important Hematology Values

Hematology Variables	Units	Definition of Potentially Clinically Important Current (Version 4) Grade 3 or Greater	
		Very Low	
Hemoglobin	g/dL	< 8.0	
Platelets count	10 ⁹ /L	< 50.0	
WBC count	10 ⁹ /L	< 2.0	
Neutrophils	10 ⁹ /L	< 1.0	
Lymphocytes	10 ⁹ /L	< 0.5	

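### The SAP's closest-to-target rule can let a laboratory retest replace an early abnormal scheduled value in the by-visit change summaries, with a modest expected pull towards normal

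*SAP*

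**What the plan says.** Protocol 5.3.1.1 (Safety Laboratory Parameters) creates the retests: "Clinically relevant abnormal laboratory test results must be confirmed using an unscheduled visit laboratory kit and should be repeated until normalization or stabilization". The same sentence lets the repeats end once some other cause accounts for the result. Confirmation is mandatory. Further repeats are a recommendation with three end points, of which return to normal is only one. SAP 4.2 also foresees extra visits: "Additional visits for the purpose of re-testing of laboratory parameters or AE monitoring may be included as deemed necessary by the investigator".

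SAP 6.0 then decides which value represents a visit. Its scope includes laboratory data: "For efficacy analyses, local tolerability, laboratory parameters, and vital sign variables, analysis windows are constructed using the following algorithm". Where a window holds several values, the rule selects by distance: "If more than one assessment is included in a time window the assessment closest to the nominal day will be used". A separate sentence settles ties in favour of the later sample. Nothing gives the scheduled sample priority or excludes unscheduled samples, and the algorithm aims to take in all data after baseline.

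SAP 11.3.2 summarises "Changes from Baseline to each scheduled visit" and to the final value by mean, standard deviation and median. Its special rules cover only several measurements on one day (average for changes, last for shift tables, worst for the grade 3 or higher outputs). None deals with a retest on a different day.

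**The concern.** The choice of analysed value depends on the value itself. A second sample in the window exists mainly because the first was abnormal enough to check. When the rule prefers the second sample, the by-visit table shows the follow-up value instead of the one that prompted the follow-up. Some of those follow-up values will have moved back towards normal, through recovery, intervention or regression to the mean.

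Safety is a primary objective. With at least 8 subjects per substudy randomised 1:1, a disease-by-dose cell holds about 4 subjects, so one substituted value can change a cell mean visibly.

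**Working it through.** The plan states no figure for this point, so there is none to reproduce.

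**1. The rule as a formula.** Let v be the scheduled visit's offset in days from the target (negative means early) and g the gap to the retest. The retest is selected if |v+g| < |v|, or if |v+g| = |v| with v+g > 0. For v ≥ 0 this never happens. For v = −d it happens exactly when g ≤ 2d.

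**2. The target day.** In the SAP window tables the target is 7 × week + 1 for Weeks 4 to 160. Protocol Appendix C lists the visit day as 7 × week. At Week 16 that is 113 against 112. A visit made exactly on schedule therefore counts as one day early, and a retest 1 or 2 days later displaces it. The SAP 6.0 text itself gives Week 4 as Rx Day 28, while its Table 1 has 29, so both readings are run below. Weeks 172, 184 and 188 do not follow the 7 × week + 1 grid (their targets are 42 days lower) and are left out.

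**3. Week 16 examples (target 113).**
- Visit on Day 106 (d = 7, 2d = 14): a retest on Day 113 or 120 replaces it; a retest on Day 121 does not.
- Visit on Day 112 (d = 1, 2d = 2): a retest on Day 114 replaces it; a retest on Day 115 does not.
- Visit on Day 116: no later retest replaces it.

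A replacing retest lies at most d days past the target. The Week 16 window runs to Day 134 in Table 1 (21 days past) and Day 155 in Table 2 (42 days past), so the window edge does not prevent it.

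**4. Share replaced, given a retest.** The documents give no distribution of visit days or retest gaps. Assumptions: visits fall evenly on whole days over a ±7 or ±3 day allowance (both appear in Appendix C), and the gap is evenly 3 to 14 days (12 values). The number of those gaps with g ≤ 2d is 0, 2, 4, 6, 8, 10, 12, 12 for d = 1 to 8.

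| Visit spread | Nominal day | v | Replaced | Share |
|---|---|---|---|---|
| ±7 | protocol day + 1 (SAP tables) | −8 to 6 | (0+2+4+6+8+10+12+12)/(15×12) = 54/180 | 30% |
| ±7 | protocol day (SAP text) | −7 to 7 | (0+2+4+6+8+10+12)/180 = 42/180 | 23% |
| ±3 | protocol day + 1 | −4 to 2 | (0+2+4+6)/(7×12) = 12/84 | 14% |
| ±3 | protocol day | −3 to 3 | (0+2+4)/84 = 6/84 | 7% |

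For the first row by fixed gap: 3 days 7/15 (47%), 7 days 5/15 (33%), 14 days 2/15 (13%), 17 days or more 0.

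**5. Effect on one cell (assumed values).** One subject has ALT 30 at baseline, 200 at the visit and 60 at the retest; the others do not change. In a cell of 4 the mean change is (200−30)/4 = +42.5 from the scheduled sample and (60−30)/4 = +7.5 from the retest. Over all 16 subjects it is 170/16 = +10.6 against 30/16 = +1.9.

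**6. Average effect (simulated, assumed inputs).** With 40% of variance within subject, a retest whenever a value lies beyond 2 SD, a gap of 3 to 14 days and the ±7 spread, 30% of the abnormal values are replaced. A true mean shift of 1.00 SD is summarised as 0.97 SD. With no true shift the mean does not move, and the SD falls from 1.00 to 0.98.

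**7. With scheduled priority,** the replaced share is 0 for every v and g.

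**The case against.** Three stronger readings are tempting, and the documents support none of them.

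- *A reader might infer that abnormal results have to be repeated until they are normal.* Only confirmation is obligatory. Repeats may also end at stabilisation or an alternative explanation, possibly with the value still abnormal.
- *A reader might infer that substitution runs only towards normal.* SAP 4.2 also allows extra visits for adverse-event monitoring, and Protocol 6.1.1.3 calls for an unscheduled blood test when hepatic symptoms appear without laboratory results. Such a draw could replace an earlier normal value with an abnormal one. A retest that confirms or exceeds the abnormality does not pull towards normal either.
- *A reader might infer that abnormalities disappear from the safety report.* SAP 11.3 and 11.3.2 separately provide the extreme on-treatment value, shifts to minimum and maximum, threshold frequencies, the grade 3 or higher listing with the whole course of the parameter, and the liver summaries and listings. None of these is defined through the by-visit selection.

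Further points stand. The shares are conditional on a retest having occurred and are not shares of all laboratory values. No hypothesis is tested, and the rule is the same in both dose arms. A retest may also correct a spurious first result, and the median is reported beside the mean.

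One might also read the reference to each scheduled visit in SAP 11.3.2 as meaning scheduled samples only. The SAP does not say so, and its Section 6.0 applies the window rule to laboratory parameters. These points limit the size and reach of the problem but leave the selection mechanism in place.

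**Conclusion.** The point holds for the by-visit laboratory change summaries only, and it is minor. Followed as written, SAP 6.0 lets a retest within 2d days replace a scheduled value taken d days early; values taken on or after the target day are never displaced by a later retest. The expected net effect is a modest pull towards normal, because abnormality is the main trigger for retesting.

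The shares in the table, from 7% to 30% of retested values, rest on assumed visit spread and retest timing. The average distortion is small. The practical risk is a single substitution dominating a mean in a cell of about 4. The final-value summary may also pick up a retest, but as the last value and not through this rule.

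**What to change.** Add to SAP 6.0, under the analysis windows: for laboratory by-visit summaries, use the sample from the scheduled visit; use an unscheduled sample in the window (closest to target) only if the scheduled one is missing. State that all samples, including retests, remain in the minimum, maximum, extreme-value, potentially clinically important and listing outputs. In the same edit, align the Rx Day 28 example in the text with the Day 29 target in Table 1.

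The cost is a sentence or two and a visit-type filter in programming. By-visit means may look slightly less favourable, and an occasional spurious first value will be kept, with its retest visible in the listings.

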
• Have a diagnosis of generalized pustular psoriasis for at least 60 days prior to informed consent based on the diagnostic criteria of the Japanese Dermatological Association (JDA). Subjects not fulfilling one of the diagnostic criteria i.e., "accompanying systemic symptoms including fever or malaise" at the time of screening can be entered.• Subjects with an erythema area with pustules accounting for \geq 10% of the body surface area (BSA), and with a severity assessment criteria score (JDA total score) specified by the JDA of less than 14.• Must be candidates for systemic therapy or phototherapy for generalized pustular psoriasis, as assessed by the investigator.	

Diagnosis and Main Criteria for Inclusion/Exclusion (Continued):**Main Inclusion (Continued):**For erythrodermic psoriasis

- Have a diagnosis of erythrodermic psoriasis prior to informed consent.
- Subjects with an inflammatory erythema area accounting for $\geq 80\%$ of the BSA at screening and at the time of the first administration of the study drug.
- Must be candidates for systemic therapy or phototherapy for erythrodermic psoriasis, as assessed by the investigator.

Main Exclusion:

1. Previous exposure to risankizumab.
2. Currently enrolled in another investigational study or less than 30 days (from screening) since completing another investigational study (participation in observational studies is permitted).

For generalized pustular psoriasis

- Subjects with active ongoing inflammatory diseases other than generalized pustular psoriasis that might confound trial evaluations according to investigator's judgment.

For erythrodermic psoriasis

- Subjects with active ongoing inflammatory diseases other than erythrodermic psoriasis that might confound trial evaluations according to investigator's judgment.
- Subject diagnosed with medication-induced or medication-exacerbated EP.

Investigational Product: Risankizumab (ABBV-066): 75 mg pre-filled syringe, 90 mg/mL, 0.83 mL dispensed volume, 0.87 mL fill volume

Doses: Risankizumab (ABBV-066): 150 mg (2 syringes, 75 mg each) or 75 mg (1 syringe) administered at Week 0, 4 and every 12 weeks

Mode of Administration: Subcutaneous injection

Duration of Treatment: 172 weeks

Criteria for Evaluation:**Efficacy:**

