5.5.2 Identity of Investigational Products

Information about the risankizumab formulation to be used in this study is presented in [Table 3](#).

Table 3. Description of Test Product Risankizumab

Substance:	Risankizumab
Pharmaceutical form:	[REDACTED]
Source:	Boehringer Ingelheim Pharma GmbH & Co. KG
Chemical form:	Anti-human IL-23p19 mAb
Molecular weight	Approximately 148 kDa
Unit Strength:	75 mg risankizumab in a pre-filled syringe, concentration 90 mg/mL
Route of administration:	Subcutaneous injection
Posology:	Week 0, Week 4, then every 12 weeks
Duration of use:	172 weeks

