	V1	V2	V3	V4	V5	V6	V7	V8	V9	V10	V11	V12	V13	V14	V15	V16	V17	V18	V19	V20	V21			
Visit	0	4	8	12	16	22	28	34	40	46	52	64	76	88	100	112	124	136	148	160	172	184	188	
Week	0	4	8	12	16	22	28	34	40	46	52	64	76	88	100	112	124	136	148	160	172	184	188	
Day	-42 to -1	1	28	56	84	112	154	196	238	280	322	364	448	532	616	700	784	868	952	1036	1120	1162	1246	1274
Visit window (days)	± 3	± 7	± 7	± 7	± 7	± 7	± 7	± 7	± 7	± 7	± 7	± 7	± 7	± 7	± 7	± 7	± 7	± 7	± 7	± 7	± 7	± 7	± 7	± 7
Last injection of trial medication ¹¹																								
Trial completion																								
Vital status ¹²																								

1. At Visit 1, all subjects at all sites will be evaluated via CASPAR for history of psoriatic arthritis as detailed in [Appendix F](#).
2. Refer to Section [5.3.1.1](#) for weight procedures.
3. Physical examination: C = complete, T = targeted. Refer to Section [5.3.1](#).
4. Vital signs should precede blood sampling and be assessed pre-dose at all dosing visits. At Visit 2 and Visit 3, additional vital sign assessments should be taken at 5 minutes post-dose and 60 minutes post-dose. Subjects should be closely monitored for signs and symptoms of hypersensitivity reactions for approximately 2 hours after the first dose administered and 1 hour following all other doses of study drug.
5. Infection screening consists of Hepatitis B Surface Antigen (qualitative), Total Hepatitis B Core Antibodies (qualitative), Hepatitis B Surface Antibody (qualitative), Total Hepatitis C Virus RNA (Quantitative) reflex, Hepatitis C Virus RNA (Qualitative), Hepatitis C Antibodies (Qualitative), Hepatitis C Antibody (Qualitative), PPD or Quantiferon-TB. Hepatitis B, Hepatitis C and HIV testing will be performed at screening, Visit 12, 16, 20 and Week 184.
6. Serum pregnancy testing in all female subjects at screening and if urine pregnancy test is positive. Urine pregnancy testing will be done in women of child-bearing potential prior to administration of study drug at all dosing visits and at each Follow-Up Visit.
7. C = complete, T = targeted. Targeted lab samples should be limited to WBC, serum CRP and serum albumin for the measurement of JDA. Subjects should be fasting for at least 8 hours prior to the blood sample being taken at the "complete" visits, except for screening. If not fasted mark on laboratory requisition form.
8. On dosing visits, PK and ADA sampling should be taken approximately within 1 hour prior to administration of study drug.
9. Collected for Substudy GPP.

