10. Collected for Substudy EP.

11. Subjects that terminate trial medication early will complete EOT Visit procedures instead of the planned treatment period visit and return for Week 188 Follow-up Visit, 16 weeks after last dose of study medication.
12. Vital Status should be collected for subjects leaving the study before the planned Week 188 Follow-up visit.

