Table 1. Visit Windows for Analysis of Clinical Laboratory Tests, Vital Signs, Local Tolerability (WBC, CRP and ALB), and Efficacy Variables (PASI/JDA Score and Responder Rating/PGA-GPP/CGI-GI/BSA)

Window Label	Target Day	Interval
Screening	–	[–42, –1]
Baseline ^a	1	≤ 1 ^b
Week 4	29	[2, 43]
Week 8	57	[44, 71]
Week 12	85	[72, 99]
Week 16	113	[100, 134]
Week 22	155	[135, 176]
Week 28	197	[177, 218]
Week 34	239	[219, 260]
Week 40	281	[261, 302]
Week 46	323	[303, 344]
Week 52	365	[345, 407]
Week 64	449	[408, 491]
Week 76	533	[492, 575]
Week 88	617	[576, 659]
Week 100	701	[660, 743]
Week 112	785	[744, 827]
Week 124	869	[828, 911]
Week 136	953	[912, 995]
Week 148	1037	[996, 1079]
Week 160	1121	[1080, 1142]
Week 172	1163	[1143, 1205]
Week 184	1247	[1206, 1261]
Week 188	1275	[1262, 1282]

Rx Day calculated relative to first dose of risankizumab. For subjects randomized but not dosed, Rx Day calculated relative to Randomization.

- a. There is no baseline for local tolerability measurements and CGI-GI.
- b. If time is collected, restrict to records prior to the first dose of study drug.

Table 2. Visit Windows for Analysis of Clinical Laboratory Tests (excluding WBC, CRP and ALB)

Window Label	Target Day	Interval
Screening	–	[–42, –1]
Baseline ^a	1	≤ 1 ^a
Week 8	57	[2, 85]
Week 16	113	[86, 155]
Week 28	197	[156, 239]
Week 40	281	[240, 323]
Week 52	365	[324, 533]
Week 100	701	[534, 869]
Week 148	1037	[870, 1100]
Week 172	1163	[1101, 1205]
Week 184	1247	[1206, 1261]
Week 188	1275	[1262, 1282]

Rx Day calculated relative to first dose of risankizumab. For subjects randomized but not dosed, Rx Day calculated relative to Randomization.

a. If time is collected, restrict to records prior to the first dose of study drug.

Table 32. Visit Windows for Analysis of Efficacy Variable (DLQI)

Window Label	Target Day	Interval
Baseline	1	$\leq 1^a$
Week 12	85	[2, 99]
Week 16	113	[100, 239]
Week 52	365	[240, 407]
Week 64	449	[408, 491]
Week 76	533	[492, 575]
Week 88	617	[576, 659]
Week 100	701	[660, 743]
Week 112	785	[744, 827]
Week 124	869	[828, 911]
Week 136	953	[912, 995]
Week 148	1037	[996, 1079]
Week 160	1121	[1080, 1142]
Week 172	1163	[1143, 1205]
Week 184	1247	[1206, 1261]
Week 188	1275	[1262, 1282]

Rx Day calculated relative to first dose of risakizumab. For subjects randomized but not dosed, Rx Day calculated relative to Randomization.

a. If time is collected, restrict to records prior to the first dose of study drug.

Definition of Missing Data Imputation

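### Weeks 172, 184 and 188 carry Day values 42 days too early in the protocol, and the SAP windows inherit the slip, so end-of-study visits held at their labelled weeks are mislabelled or fall in no window

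*SAP*

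**What the plan says.** The schedule in protocol Appendix C has a Week row and a Day row. The Week row ends "136 148 160 172 184 188" and the Day row ends, for the same six columns, "952 1036 1120 1162 1246 1274". The visit window for these late visits is ±7 days.

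The protocol describes treatment length and dosing in weeks. The Synopsis has "Duration of Treatment: 172 weeks", and Table 3 in section 5.5.2 gives the posology as "Week 0, Week 4, then every 12 weeks". A footnote to Appendix C has subjects who stop drug early "return for Week 188 Follow-up Visit, 16 weeks after last dose of study medication".

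SAP 4.2, repeating protocol 5.1, states: "Each visit date (with its window) is to be counted from Day 1". SAP 6.0 then sets analysis windows around target days in three tables. In Table 1 and the DLQI table, Week 160 has target 1121 and window [1080, 1142]. All three tables share the last three rows' targets:

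- Week 172: "Week 172 1163 [1143, 1205" in Table 1 and the DLQI table; in Table 2 the window is [1101, 1205]
- Week 184: target 1247, window [1206, 1261]
- Week 188: target 1275, window [1262, 1282]

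No window extends beyond Day 1282.

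**The concern.** The Week and Day rows of Appendix C cannot both be right for the last three columns, and the SAP windows are built on the Day row while keeping the week labels. Sites therefore have two calendars for the end of the study, and the analysis recognises only one of them.

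If visits follow the week labels, on-time Week 184 and Week 188 assessments belong to no analysis visit. For efficacy this is more than an omission, because a value outside every window becomes missing and goes through the imputation rules in SAP 6.0. A binary endpoint with no later windowed assessment is imputed as failure, and a continuous endpoint takes an earlier value by LOCF. By-visit laboratory and vital-sign summaries would lose the follow-up after treatment.

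If visits follow the Day row, the assessments are all captured, but under labels that are six weeks too late. The stated treatment duration would also be wrong. The study's stated aim is long-term safety and efficacy in about 16 subjects, roughly four per arm per substudy, so each misclassified subject is visible in the tables.

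**Working it through.** **1. Conventions.** From Week 4 to Week 160, the Appendix C Day is 7 x week and the SAP target is 7 x week + 1. All 19 post-baseline visits in that range match exactly. For example, Week 160 gives 7 x 160 = 1120 in the protocol and 1121 in the SAP. (The SAP text illustrates Week 4 as Rx Day 28 while Table 1 uses 29. This one-day difference is covered in step 5.)

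**2. The last three visits.**

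| Week | 7 x week | Protocol Day | 7 x week + 1 | SAP target | Difference | Stated Day / 7 |
|---|---|---|---|---|---|---|
| 172 | 1204 | 1162 | 1205 | 1163 | -42 | Week 166 |
| 184 | 1288 | 1246 | 1289 | 1247 | -42 | Week 178 |
| 188 | 1316 | 1274 | 1317 | 1275 | -42 | Week 182 |

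The steps in the Day row are 1162 - 1120 = 42 days (12 weeks would be 84), then 1246 - 1162 = 84 and 1274 - 1246 = 28, both correct. This is one slip, carried forward.

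**3. Which row the rest of the protocol supports.** Doses at Weeks 0 and 4 and then every 12 weeks give 4 + 14 x 12 = 172, so Week 172 lies on the dosing grid and matches the 172-week duration. Day 1162 (Week 166) matches neither. The 16-week gap to the last follow-up does not discriminate: 188 - 172 = 16 weeks, and 1274 - 1162 = 112 days = 16 weeks.

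**4. The SAP windows reproduced.** The upper bound is the midpoint of adjacent targets, and the last window ends at target + 7:

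- Week 160: (1121 + 1163)/2 = 1142
- Week 172: (1163 + 1247)/2 = 1205
- Week 184: (1247 + 1275)/2 = 1261
- Week 188: 1275 + 7 = 1282
- Table 2, Week 148: (1037 + 1163)/2 = 1100

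This rule reproduces every window in Tables 1 and 2, so the bounds inherit the slip.

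**5. Where visits held at the labelled week would fall** (±7 days, 15 permitted days each):

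| Visit | Centre 7 x week + 1 | Centre 7 x week |
|---|---|---|
| Week 172 | 1198-1212: 8 days labelled Week 172, 7 labelled Week 184 | 1197-1211: 9 labelled Week 172, 6 labelled Week 184 |
| Week 184 | 1282-1296: 1 labelled Week 188, 14 in no window | 1281-1295: 2 labelled Week 188, 13 in no window |
| Week 188 | 1310-1324: 15 in no window | 1309-1323: 15 in no window |

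**6. If sites follow the Day row.** Days 1163, 1247 and 1275, each ±7, lie wholly inside their stated windows, so nothing is lost. The visits take place at Weeks 166, 178 and 182.

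**The case against.** The arithmetic is not in dispute, and the same figures in three SAP tables rule out a PDF artefact. The case on the other side concerns importance and certainty.

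- **Limited reach.** The primary endpoints are at Week 16 and the secondary endpoints at Weeks 16 and 52. The planned interim analyses at Weeks 28 and 52 are untouched, and no hypothesis is tested. Adverse-event analyses do not use these windows. Shifts to minimum, maximum and final values, potentially clinically significant values and the listings are not by-visit summaries. All of this stands: the damage is confined to descriptive by-visit results from the last part of the study.
- **Conditional harm.** Data are lost only if sites schedule by week label. Counting visits from Day 1 is compatible with either row, and the documents do not show which one sites or the IRT used. This also stands, but the other branch leaves wrong labels, duration and interval, so neither reading makes both documents correct.
- **Convention.** The exact counts depend on whether visits are centred on 7 x week or one day later. They move by one day at Weeks 172 and 184 and not at all at Week 188, so the conclusion does not change.
- **Which measures are collected.** Column alignment in Appendix C is lost in the text available here, so it does not confirm which efficacy measures are taken at Weeks 184 and 188. The SAP does set windows for them at both visits.

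**Conclusion.** The concern holds. The Appendix C Day values for Weeks 172, 184 and 188 are each 42 days short of their labels, and all three SAP window tables carry this forward.

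Assume visits at the labelled week ±7 days. Then 6 to 7 of 15 permitted Week 172 days are labelled Week 184, 13 to 14 of 15 Week 184 days fall in no window, and all 15 Week 188 days do. An on-time or early Week 172 visit keeps its correct label. Read literally, the imputation rules would record responders seen on time at Weeks 184 and 188 as failures, provided the endpoint is collected and summarised at those visits.

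The week labels have better support, from the 12-week interval and the 172-week duration, but the choice is the sponsor's. Although the main endpoints are safe, this must be corrected because the tables as written cannot classify the end-of-study visits that the protocol names.

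**What to change.** Reconcile the Week and Day rows of Appendix C, and confirm which schedule sites and the IRT have been using.

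If the week labels stand, the Appendix C days become 1204, 1288 and 1316. The SAP rows, by the SAP's own midpoint rule, become:

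| Window | Target | Table 1 and DLQI table | Table 2 |
|---|---|---|---|
| Week 148 | 1037 | unchanged | [870, 1121] |
| Week 160 | 1121 | [1080, 1163] | not in table |
| Week 172 | 1205 | [1164, 1247] | [1122, 1247] |
| Week 184 | 1289 | [1248, 1303] | [1248, 1303] |
| Week 188 | 1317 | [1304, 1324] | [1304, 1324] |

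The new bounds are (1121 + 1205)/2 = 1163, (1205 + 1289)/2 = 1247, (1289 + 1317)/2 = 1303, 1317 + 7 = 1324 and, for Table 2, (1037 + 1205)/2 = 1121.

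If the Day row stands, the SAP windows can stay, but the visits should be relabelled Weeks 166, 178 and 182, and the treatment duration and dosing interval corrected throughout both documents.

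The cost is four rows in each SAP window table and a clarification of the Appendix C Day row. No new data are needed if this is done before database lock.
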